4 TRIAL DESIGN

4.1 Overall Trial Design

This trial is a phase 3, multi-center, randomized, double-masked, saline-controlled trial to evaluate the effect of NOV03 (100% perfluorohexyloctane) at a QID dosing regimen on signs and symptoms of Dry Eye Disease. Approximately 560 male and female subjects (280 each arm) of at least 18 years of age with a subject-reported history of DED in both eyes and who meet all other trial eligibility criteria will be randomized, stratified by clinical site and dryness score <70 vs \geq 70 (VAS) at baseline, 1:1 to receive 1 of 2 treatments:

Treatment 1: NOV03 (100% perfluorohexyloctane), 4 times daily (QID)

Treatment 2: Saline (0.6% sodium chloride solution), QID

Each treatment group will be comprised of 280 subjects such that approximately 250 evaluable subjects per arm complete the trial. Approximately 29 clinical sites are anticipated to participate.

This trial will consist of two periods: Up to 14-day screening period and a 57-day treatment period (See [Appendix 1](#)).

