5.3 Inclusion Criteria

Subjects will be eligible to participate in this trial if they **meet all** following criteria:

1. Be at least 18 years of age at the time of consent.
2. Provide written informed consent.
3. Have a subject reported history of Dry Eye Disease in both eyes for at least 6 months prior to Visit 0.
4. Have Tear film break-up time (TFBUT) ≤ 5 sec at Visit 0 and Visit 1.
5. Have Ocular Surface Disease Index (OSDI[®]) ≥ 25 at Visit 0 and Visit 1.
6. Have an unanesthetized Schirmer's Test I ≥ 5 mm at Visit 0 and Visit 1.
7. Have Meibomian Gland Dysfunction (MGD) defined as total MGD score ≥ 3 (secretion of 5 central glands on lower eyelid will be evaluated, each will be scored from 0-3; 0 = normal, 1 = thick/yellow, whitish, particulate 2 = paste; 3 = none/occluded; total score will range from 0-15) at Visit 0 and Visit 1.
8. Have a total corneal fluorescein staining score of $4 \leq X \leq 11$ (i.e. sum of inferior, superior, central, nasal, and temporal) according to the National Eye Institute (NEI) scale at Visit 0 and Visit 1.

9. Have at least one eye (the same eye) satisfy all criteria for 4, 6, 7, and 8 above at Visit 0 and Visit 1.
10. Be able and willing to follow instructions, including participation in all trial assessments and visits.

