10.3 Sample Size

The study has been designed to have at least 95% power to reject both H_{01} and H_{02} assuming independence between the sign and symptom endpoint; positive correlation between these two endpoints would increase the overall power.

Two hundred fifty (250) subjects (study eyes) per treatment group yields 97.9% power to reject H_{01} in favor of H_{A1} and conclude superiority of NOV03 over saline in the mean CFB tCFS score at Day 57 assuming a true difference (NOV03 minus saline) of -1.0, a common standard deviation of 2.8, and a two-sided alpha = 0.05. Two hundred fifty (250) subjects per treatment group yields 97.9% power to reject H_{02} in favor of H_{A2} and conclude superiority of NOV03 over saline in the mean CFB Dryness Score (VAS) at Day 57 assuming a true difference (NOV03 minus saline) of -10, a common standard deviation of 28, and a two-sided alpha = 0.05. Accounting for an assumed 10% subject discontinuation rate, approximately 560 subjects (280 subject each arm) will be randomly assigned to trial treatment such that approximately 250 evaluable participants per arm complete the trial.

Therefore, assuming independence between tCFS score and Dryness Score (VAS), 250 FAS subjects per treatment group at Day 57 yields $97.9\% * 97.9\% = 95.8\%$ power to reject both H_01 and H_02 .

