10.4.2 Unit of Analysis

For efficacy endpoints, the unit of analysis will be the study eye as defined by the following:
Study Eye: Eyes are eligible for analysis if they meet all of the inclusion criteria. In the case that both eyes are eligible for analysis, the worst eye shall be chosen, and this will be defined as the eye with worse (higher) total corneal staining at Visit 1. If the total corneal staining is the same in both eyes then the right eye will be selected as the study eye.

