10.4.5 Primary Efficacy Analyses

The primary comparisons in this trial will be between NOV03 versus saline at Day 57 in the FAS with available data per subject using the following estimands:

- Population: Subjects with DED defined through enrollment criteria
- Endpoint:
 - CFB in tCFS in the study eye at Day 57
 - CFB of Dryness Score (VAS) at Day 57
- Intercurrent event:
 - Discontinuation of study medications is ignored. [treatment policy strategy]
 - Non-optimal compliance is ignored. [treatment policy strategy]

- Withdrawal due to any reason. Missing data not imputed. [hypothetical strategy]
- Population-level summary:
 - Difference in the mean CFB in tCFS in the study eye at Day 57 between NOV03 and saline.
 - Difference in the mean CFB of Dryness Score (VAS) at Day 57 between NOV03 and saline.

If the overall study discontinuation rate is $\geq 5\%$ then the primary analysis will be based on imputation methodology using the following estimands and the available data analyses will become robustness analyses.:

- Population: Subjects with DED defined through enrollment criteria
- Endpoint:
 - CFB in tCFS in the study eye at Day 57
 - CFB of Dryness Score (VAS) at Day 57
- Intercurrent event:
 - Discontinuation of study medications is ignored. [treatment policy strategy]
 - Non-optimal compliance is ignored. [treatment policy strategy]
 - Withdrawal due to lack of efficacy or adverse events. Baseline observation carried forward (BOCF) is used to impute missing data [hypothetical strategy].
 - Missing data without withdrawal or withdrawal due to reasons other than lack of efficacy or adverse events. Multiple imputations using randomized treatment-based Markov Chain Monte Carlo is used to impute missing data [hypothetical strategy].
- Population-level summary:
 - Difference in the mean CFB in tCFS in the study eye at Day 57 between NOV03 and saline.
 - Difference in the mean CFB in Dryness Score (VAS) at Day 57 between NOV03 and saline.

The primary comparison in this trial will be between NOV03 versus saline at Day 57. The primary efficacy endpoints (e.g. CFB in total corneal fluorescein staining [NEI scale] and Dryness Score) will be tested using hierarchical fixed sequence testing and summarized descriptively (n, mean, standard deviation, median, min, and max) and analyzed separately using an ANCOVA model with terms for baseline value, and treatment.

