6.5.8.3 Study Baseline

Baseline measures are defined as the last non-missing measure prior to the initiation of randomized study treatment as documented in the subject dosing diary. Per the schedule of assessments in the protocol, this is expected to be the Visit 1 value. Measurements that are obtained after the first dose of randomized study treatment will be considered post-baseline values. If a measurement of a variable is not made on a given subject prior to the first dose of randomized study treatment, then that subject will be considered not to have a baseline value for that variable. CFB is defined as post-baseline assessment minus baseline assessment.

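### The tCFS models leave out the Visit 0 staining score that every correctly enrolled study eye has; adding it as a second covariate is a small, nearly free gain in precision

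*Protocol*

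**What the plan says.** Inclusion criterion 8 (Protocol 5.3) requires a tCFS of 4 to 11 "according to the National Eye Institute (NEI) scale at Visit 0 and Visit 1". Criterion 9 requires one and the same eye to meet this and the other ocular criteria at both visits. Both schedules of assessments (Protocol Appendix 1, SAP Table 1) place corneal staining at Visits 0 and 1. The Dryness Score is first scheduled at Visit 1.

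Baseline is the last non-missing value before treatment (Protocol 10.4.1). SAP 6.5.8.3 adds: "Per the schedule of assessments in the protocol, this is expected to be the Visit 1 value". When both eyes qualify, the worse one becomes the study eye, and "this will be defined as the eye with worse (higher) total corneal staining at Visit 1" (Protocol 10.4.2).

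The two primary endpoints are "analyzed separately using an ANCOVA model with terms for baseline value, and treatment" (Protocol 10.4.5). SAP 6.5.7.3 and 6.5.8.5 repeat this, with one baseline term in the sample code. The repeated-measures model and the sample imputation code also carry a single baseline term.

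**The concern.** The one staining covariate is a noisy reading that has also served as an entry gate and, for subjects with two qualifying eyes, as the selector of the worse eye. It therefore tends to sit above the eye's usual level. A second reading of the same eye, taken at most 14 days earlier, is on file. It helps decide which eyes are eligible but does not choose between two qualifying eyes. If it carries information about Day 57 staining beyond what Visit 1 gives, leaving it out makes the residual variance larger than necessary.

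tCFS at Day 57 is the first test in the fixed sequence: if it fails, neither Dryness nor any secondary endpoint can be claimed. Precision there is worth having when it costs nothing to collect.

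**Working it through.** **Inputs.** Protocol 10.3: "Two hundred fifty (250) subjects (study eyes) per treatment group yields 97.9% power to reject" the tCFS null hypothesis, "assuming a true difference (NOV03 minus saline) of -1.0, a common standard deviation of 2.8, and a two-sided alpha = 0.05". Allocation is "1:1 to receive 1 of 2 treatments" (Protocol 4.1). The synopsis derives the SD from an ANCOVA with baseline as covariate in NVU-002 (2.5, raised to 2.8), so 2.8 is read here as the SD remaining after adjustment for Visit 1. Correlations among Visit 0, Visit 1 and Day 57 tCFS are not in the documents; all values below are assumptions.

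**1. The plan's own figure.** SE = 2.8 × √(2/250) = 0.2504. Power = Φ(1.0/0.2504 − 1.96) = Φ(2.033) = 97.9%, as stated (97.86% by the noncentral t). For both primaries, 0.979 × 0.979 = 95.8%, as stated. The 95% CI half-width is 1.96 × 0.2504 = 0.491.

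**2. What a second covariate does.** Let a = corr(Visit 0, Visit 1), b = corr(Visit 1, Day 57), c = corr(Visit 0, Day 57). The residual variance is multiplied by f = 1 − r², where r = (c − ab) / √[(1 − a²)(1 − b²)].

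| a | b | c | r | f |
|---|---|---|---|---|
| 0.6 | 0.5 | 0.5 | 0.2/0.693 = 0.289 | 0.917 |
| 0.5 | 0.4 | 0.4 | 0.2/0.794 = 0.252 | 0.937 |
| 0.7 | 0.6 | 0.55 | 0.13/0.571 = 0.228 | 0.948 |
| 0.6 | 0.5 | 0.4 | 0.1/0.693 = 0.144 | 0.979 |
| 0.6 | 0.5 | 0.3 | 0 | 1.000 |

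The last row is serial decay (c = ab): Visit 0 then adds nothing. At the other extreme, if all three readings are equally correlated, f = (1 + 2ρ)/(1 + ρ)², which is 0.947 at ρ = 0.3 and 0.830 at ρ = 0.7. That treats Visit 0 as being as close to Day 57 as Visit 1 is, so it is an optimistic limit.

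**3. Simulation under the entry rules.** Assumed: latent tCFS mean 7, SD 2.0-2.5; measurement SD 1.0-1.5; Day 1 to Day 57 drift SD 1.8-2.3; between-eye correlation 0.7; integer scores; the 4-11 gate at both visits; the worse-eye rule at Visit 1. Variance removed by adding Visit 0:
- no true change between Visits 0 and 1: about 5.5-6%;
- drift of one quarter of the Day 1-57 drift variance (roughly proportional to a 14-day gap): about 3-4%;
- drift of one half: about 2-3%.

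Individual settings spread a little wider (1.4% to 7.1% overall). With exchangeable visits and other variance splits, the cut ran from 4% to 15%; the top value needs correlations near 0.64 and a residual SD of 1.87, well below 2.8. A range of 2-6% is used below.

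**4. Effect on the planned test.**
- 2% cut: SD = 2.8 × √0.98 = 2.772; SE 0.2479; power Φ(2.073) = 98.1%; half-width 0.486 (1.0% narrower); equivalent to 250 × 0.98 = 245 per arm.
- 6% cut: SD = 2.8 × √0.94 = 2.715; SE 0.2428; power Φ(2.158) = 98.5%; half-width 0.476 (3.0% narrower); equivalent to 250 × 0.94 = 235 per arm.

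Power for both primaries moves from 95.8% to 0.981 × 0.979 = 96.0% or 0.985 × 0.979 = 96.4%.

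**5. Validity of the planned model.** In simulation the chosen eye's Visit 1 mean exceeded its Visit 0 mean by 0.3-0.5 points with no true change, so the selection effect is real. It did not reach the contrast: the estimate was −0.987 with Visit 1 alone and −0.984 with both readings. The rejection rate of the Visit 1 ANCOVA under no effect was 0.0415 in 2,000 runs (Monte Carlo SE about 0.005), which shows no inflation.

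**The case against.** The strongest reply is that nothing is broken. A pre-specified ANCOVA on one baseline is complete and valid, and planned power is already 97.9% on figures discounted from NVU-002 (−1.2, SD 2.5). That stands, and it is why this is an improvement and not a defect. Larger power gains can be shown by supposing a true effect of −0.7, but no such effect appears in the documents.

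The two readings may also not be replicates. Eye drops are barred for 24 hours before Visit 1 (Protocol 5.4, criterion 15; 8.2), with no matching washout before Visit 0. This is fair and may shrink the gain. It does not make the covariate harmful: a separate term lets the data set its weight, and with no added information the loss is one degree of freedom among about 500.

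A reader might infer more than the documents support:
- *That worse-eye selection and regression to the mean bias the result.* Selection precedes treatment and acts on both arms alike. It can exaggerate change within each arm, but not the difference between arms.
- *That Visit 0 is thrown away or has no role in eye selection.* It gates eye eligibility, settles the study eye if only one eye passes at Visit 0, and is the fallback baseline under the last-non-missing rule. It is absent only as an additional term in the models.
- *That the same gain applies to tCFS at Day 15 and central staining at Day 57.* No gain has been computed for either. Central staining is a single 0-3 grade with no entry gate of its own.

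**Conclusion.** The point holds as a precision improvement to the tCFS analysis, with no bias or type I error problem in the plan as written. The likely size is 2-6% of residual variance, equivalent to about 5-15 subjects per arm at the planned 250. This range rests on assumed correlations and a modest true change in staining between Visits 0 and 1; under pure serial decay the gain is nil. The practical benefit is a slightly narrower interval and a little more margin if the effect is smaller or the SD larger than planned. It should not hold up the plan, but it is worth adopting while the SAP can still be amended.

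**What to change.** Before unmasking, by SAP amendment and matching protocol text:

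1. Add the study-eye Visit 0 tCFS, taken from the screening at which the subject qualified, as a second continuous covariate in the tCFS ANCOVA (Protocol 10.4.5; SAP 6.5.7.3 and 6.5.8.5). Naming the qualifying screening settles which record applies after a re-screen.
2. Add it to the repeated-measures sensitivity model.
3. Add it to the MCMC imputation model, which becomes primary if discontinuation reaches 5%. The plan itself expects that branch: "Accounting for an assumed 10% subject discontinuation rate". The sample code works by corneal region, so the Visit 0 score for the same region is the natural term.
4. State a rule for a missing Visit 0 value, for example using the Visit 1 value, so that no FAS subject drops out of the model.
5. Leave change from baseline as defined, and leave the Dryness models alone, since Dryness is not scheduled at Visit 0.

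The same change may be made for tCFS at Day 15 and, with the Visit 0 central score, for central staining at Day 57, without claiming a size for the gain.

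The cost is one degree of freedom, edits to three models and one missing-value rule. No new data or visits are needed.

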10.4.6 Secondary Efficacy Analyses

The following secondary endpoints will be tested hierarchically:

1. CFB of Dryness Score (VAS) at Day 15.
2. CFB in tCFS (NEI scale) at Day 15.
3. CFB VAS burning/stinging at Day 57.
4. CFB in central Corneal Fluorescein Staining (cCFS) (NEI scale) at Day 57.

Inference will only be made on these endpoints, at a 2-sided alpha = 0.05, if both primary endpoints and any higher order secondary endpoints are statistically significant at a 2-sided alpha = 0.05 in favor of NOV03.

Quantitative secondary efficacy endpoints will be summarized similarly to the primary efficacy endpoints.

The primary analysis of the secondary endpoints will use the FAS with available data per subject, assuming the overall study discontinuation rate is <5%. If the overall study discontinuation rate is $\geq 5\%$, then the primary analysis of the secondary endpoints will be based on imputation methodology as defined in [Section 10.4.5](#) and the available data analyses will become robustness analyses.

10.4.7 Other Pre-specified Efficacy Analyses

The analyses of other pre-specified endpoints will use the Full Analysis Set (FAS) with available data per subject.

1. CFB of Dryness Score (VAS) at Day 29.
2. CFB in tCFS at Day 29.
3. CFB in CFS central and inferior sub-regions (NEI scale) to each measured post-baseline visit.
4. Proportion of tCFS responders (≥ 3 improvement based on NEI scale) at Day 57.
5. Proportion of Dryness Score responders ($\geq 30\%$ improvement from baseline) at Day 57.
6. CFB in VAS burning/stinging, sticky feeling, foreign body sensation, itching, blurred vision, sensitivity to light, pain, frequency of dryness, and awareness of dry eye symptoms at each measured post-baseline visit.
7. CFB in Ocular Surface Disease Index (OSDI[®]) at each measured post-baseline visit.

Quantitative other pre-specified efficacy endpoints will be summarized descriptively (n, mean, standard deviation, median, min and max) by visit, and analyzed similarly to the primary endpoint at each measured visit. Least squares mean for each treatment group and

for the difference between treatment groups will be presented from the model together with two-sided p-values and 95% confidence intervals.

Two-sample t-tests, Wilcoxon rank sum tests and mixed-effect repeated measures analysis will also be presented as sensitivity analyses.

Other pre-specified endpoints evaluating the proportion of study eyes (or subjects) meeting pre-defined criteria will be presented and tested between treatment groups using logistic regression analysis adjusting for baseline tCFS score at each measured follow-up visit. Pearson chi-squared analysis comparing the treatment groups will be performed as sensitivity analyses.

Exploratory and other endpoints will be summarized and analyzed similarly to the other pre-specified endpoints.

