The statistical hypotheses for the hierarchical primary endpoint of the CFB Dryness Score (VAS) at Day 57 are as follows:

H_{02} : The difference, between subjects treated with NOV03 and subjects treated with saline, in the mean CFB Dryness Score (VAS) at Day 57 = 0.

H_{A2} : The difference, between subjects treated with NOV03 and subjects treated with saline, in the mean CFB Dryness Score (VAS) at Day 57 $\neq 0$, with superiority claimed if the difference is less than 0 (NOV03 minus saline).

The study has been designed to have 95% power to reject both H_{01} and H_{02} assuming independence between the sign and symptom endpoint; positive correlation between these two endpoints would increase the overall power.

Estimated mean differences (common standard deviations) in CFB to Day 57 using an ANCOVA analysis with CFB to Day 57 as the response, baseline as a covariate and treatment as the fixed effect from NVU-002 are: -1.2 (2.5) for tCFS and -11 (26) for Dryness Score. Conservative estimates of -1.0 (2.8) for tCFS and -10 (28) for Dryness Score are used for sample size calculation.

Two hundred fifty (250) subjects (study eyes) per treatment group yields 97.9% power to reject H_{01} in favor of H_{A1} and conclude superiority of NOV03 over saline in the mean CFB tCFS score at Day 57 assuming a true difference (NOV03 minus saline) of -1.0, a

common standard deviation of 2.8, and a two-sided alpha = 0.05. Two hundred fifty (250) subjects per treatment group yields 97.9% power to reject H_{02} in favor of H_{A2} and conclude superiority of NOV03 over saline in the mean CFB Dryness Score (VAS) at Day 57 assuming a true difference (NOV03 minus saline) of -10, a common standard deviation of 28, and a two-sided alpha = 0.05. Accounting for an assumed 10% subject discontinuation rate, approximately 560 subjects (280 subject each arm) will be randomly assigned to trial treatment such that approximately 250 evaluable participants per arm complete the trial.

Therefore, assuming independence between tCFS score and Dryness Score (VAS), 250 FAS subjects per treatment group at Day 57 yields $97.9\% * 97.9\% = 95.8\%$ power to reject both H_{01} and H_{02} .

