Other pre-specified endpoints evaluating the proportion of study eyes (or subjects) meeting pre-defined criteria will be presented and tested between treatment groups using logistic regression analysis adjusting for baseline tCFS score at each measured follow-up visit. Pearson chi-squared analysis comparing the treatment groups will be performed as sensitivity analyses.

Safety Variables:

Adverse events (AEs) will be coded using the MedDRA dictionary. Frequencies and percentages of subjects with treatment-emergent adverse events (TEAEs), serious TEAEs, and TEAEs causing premature discontinuation will be provided by treatment group. An AE is treatment emergent if it occurs or worsens after the first dose of trial treatment. Furthermore, frequencies will be given of subjects with TEAEs by system organ class; by system organ class and preferred term; by system organ class, preferred term and maximal severity; by system organ class, preferred term and strongest relationship; and by system organ class, preferred term, maximal severity, and strongest relationship. Separate summaries will be performed for ocular and non-ocular TEAEs. Other safety endpoints including assessments of visual acuity, slit-lamp biomicroscopy, dilated fundoscopy, and intraocular pressure will be summarized by treatment group and visit using descriptive statistics. Changes from baseline will also be summarized where appropriate. For assessments performed by eye, study eye and fellow eye will be summarized separately.

TABLE OF CONTENTS

1	SYNOPSIS AND TRIAL CONTACT INFORMATION.....	2
1.1	TRIAL CONTACT INFORMATION.....	2
1.2	SYNOPSIS	3
	TABLE OF CONTENTS	13
	LIST OF ABBREVIATIONS	17
2	INTRODUCTION.....	19
2.1	Dry Eye Disease (DED)	19
2.2	Product Rationale.....	19
2.3	Trial Rationale.....	20
2.4	Summary of Known and Potential Risks and Benefits to Human Subjects ...	21
3	TRIAL OBJECTIVES.....	22
3.1	Primary Objective	22
3.2	Secondary Objectives	22
4	TRIAL DESIGN.....	22
4.1	Overall Trial Design	22
4.2	End of Trial Definition.....	23
4.3	Visit Description	23
4.4	Enrollment and Treatment Assignment.....	24
4.5	Justification of Trial Design	25
4.6	Justification of Dose	26
5	TRIAL POPULATION	26
5.1	Number of Subjects (approximate).....	26
5.2	Trial population characteristics	26
5.3	Inclusion Criteria	26
5.4	Exclusion Criteria.....	27
5.5	Re-Screen Procedures	28
5.6	Subject/Trial Withdrawal Criteria	29
6	TRIAL PARAMETERS	30
6.1	Efficacy Endpoints	30
6.1.1	Primary Efficacy Endpoints:.....	30

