6.5.4.1.1 Dryness Score

Baseline dryness score will be summarized using descriptive statistics by treatment group and overall. Assessment for both eyes is done simultaneously.

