6.5.7.4.2 Other Pre-specified Efficacy Analyses

The other pre-specified efficacy analyses will use the FAS with available data per subject:

[figure not shown]
1. CFB of Dryness Score (VAS) at Day 29
2. CFB in tCFS at Day 29
3. CFB in CFS central and inferior sub-regions (NEI scale) to each measured post-baseline visit
4. Proportion of tCFS responders (≥ 3 improvement based on NEI scale) at Day 57
5. Proportion of Dryness Score responders ($\geq 30\%$ improvement from baseline) at Day 57
6. CFB in VAS burning/stinging, sticky feeling, foreign body sensation, itching, blurred vision, sensitivity to light, pain, frequency of dryness, and awareness of dry eye symptoms at each measured post-baseline visit
7. CFB in OSDI at each measured post-baseline visit

Quantitative efficacy variables will be summarized descriptively (n, mean, standard deviation, median, min and max) by visit, and analyzed similarly to the primary endpoint at each measured visit. Least squares mean for each treatment group and for the difference between treatment groups will be presented from the model together with two-sided p-values and 95% confidence intervals. For assessments performed by eye, study eye and fellow eye will be summarized separately.

Endpoints evaluating the proportion of study eyes (or subjects) meeting pre-defined criteria will be presented and tested between treatment groups using logistic regression analysis adjusting for baseline tCFS score at each measured follow-up visit.

Sample SAS logistic regression code:

```
PROC LOGISTIC DATA=INDATA DESCENDING;
  CLASS <TREATMENT>;
  MODEL <ENDPOINT>=<TREATMENT> <BASELINE>;
RUN;
```

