6.5.8.5 Adjustment for Covariates

The primary endpoints are CFB in total corneal fluorescein staining (NEI scale) at Day 57 and CFB of Dryness Score (VAS) at Day 57. The two primary endpoints will be analyzed separately using an ANCOVA model with baseline measurement as a numeric covariate and treatment as the main effect.

Subject randomization is stratified by clinical site and dryness score <70 vs ≥ 70 (VAS) at baseline (Visit 1). The analyses will not be adjusted for the stratification factors.

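### Dryness Score responders are adjusted for baseline tCFS only; adding baseline Dryness Score to that model is a small, nearly free improvement and not the correction of an error

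*Protocol*

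**What the plan says.** Protocol 10.4.7 lists two responder endpoints at Day 57: tCFS responders (improvement of at least 3 on the NEI scale) and Dryness Score responders (improvement of at least 30% from baseline). One sentence sets the model for both. They are to be "tested between treatment groups using logistic regression analysis adjusting for baseline tCFS score at each measured follow-up visit". The Protocol synopsis repeats it ("logistic regression analysis adjusting for baseline tCFS score at each measured follow-up visit"), and so does SAP 6.5.7.4.2 ("using logistic regression analysis adjusting for baseline tCFS score"). The sample PROC LOGISTIC code in that SAP section has only a generic `<BASELINE>` term, which is not defined.

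The continuous endpoints are handled differently. Protocol 10.4.5 has each primary endpoint "analyzed separately using an ANCOVA model with terms for baseline value, and treatment", and SAP 6.5.8.5 says: "The two primary endpoints will be analyzed separately using an ANCOVA model with baseline measurement as a numeric covariate". The mean change in Dryness Score is therefore adjusted for baseline Dryness Score. On how the score is rated, SAP 6.5.4.1.1 says: "Assessment for both eyes is done simultaneously". It belongs to the subject, whereas tCFS belongs to the study eye.

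**The concern.** The two Dryness results, mean change and responders, are conditioned on different baselines. The responder model adjusts a symptom for a corneal sign in one eye and leaves out the symptom's own baseline, which is collected at Visit 1. If baseline Dryness Score predicts response, a little power is given up for nothing. Protocol 4.6 cites responder analyses from NVU-002 as showing the relevance of the observed changes, so the result will be read.

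There is also a programming risk. `<BASELINE>` appears in both the primary PROC GLM code (SAP 6.5.7.3) and the PROC LOGISTIC code. In the first it means the endpoint's own baseline. In the second the surrounding text makes it baseline tCFS. A programmer who carries the first meaning into the Dryness responder table (14.2.10.1) would depart from the SAP text without noticing.

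**Working it through.** **Inputs from the documents.** 250 per arm, Dryness difference -10, SD 28, two-sided alpha 0.05 (Protocol 10.3); response means at least 30% improvement; randomisation stratified at Dryness Score 70.

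**The plan's own figure.** z = 10 / (28 × √(2/250)) = 10 / 2.504 = 3.993, and Φ(3.993 − 1.960) = 97.9%, as stated. The joint figure 0.979 × 0.979 = 95.8% also reproduces. Neither is affected by this point. The documents give no power for the responder analysis.

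**When baseline Dryness can help.** Let B be baseline, with mean 65, and let the mean change in the saline arm be −18 + s(B − 65), where s is the slope of change on baseline. A subject responds if the fall is at least 0.3B. The net dependence of response on B is therefore (−s − 0.3)B. It is zero at s = −0.3 and grows as s moves away in either direction. Because response is already scaled to baseline, a weak dependence is a realistic case.

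**Simulation.** Assumed, not in the documents: baseline Dryness mean 65 and SD 20, saline change about −18, SD 28 taken as the residual SD, Day 57 scores limited to 0–100. Here tCFS has no effect of its own on Dryness change, and its correlation with baseline Dryness is 0 or 0.3. There were 3,000 trials per row. Saline response was about 48% and NOV03 response 61% to 62%.

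| Slope s | Correlation of tCFS with baseline Dryness | Correlation of B with response | Power, tCFS (planned) | Power, Dryness | Power, both |
|---|---|---|---|---|---|
| +0.2 | 0 | −0.26 | 85.9% | 87.5% | 87.5% |
| 0 | 0 | −0.16 | 88.8% | 89.1% | 88.9% |
| 0 | 0.3 | −0.16 | 88.5% | 88.9% | 89.0% |
| −0.3 | 0 | 0.00 | 88.8% | 89.0% | 88.9% |
| −0.3 | 0.3 | 0.00 | 88.9% | 89.1% | 88.8% |
| −0.6 | 0 | +0.16 | 88.0% | 88.4% | 88.4% |
| −0.6 | 0.3 | +0.16 | 87.6% | 87.9% | 87.7% |

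Replacing tCFS by Dryness gains 0.2 to 1.6 points; using both changes power by −0.1 to +1.6. When percentage change is made independent of baseline, the swap gives 88.8% against 88.9%, which is no gain.

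**Where the gain comes from.** The standard error does not shrink; the log odds ratio moves. At s = +0.2 the mean estimate over its standard error goes from 0.546/0.182 = 3.00 to 0.586/0.189 = 3.10. At s = −0.3 it is 0.574/0.182 = 3.15 in both models.

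**If tCFS is itself prognostic.** Let baseline tCFS correlate about −0.2 with Dryness change (assumed; unstratified allocation; 3,000 trials). Power with tCFS, then with Dryness, is 88.0/87.8% at s = 0, 89.5/88.5% at s = −0.3 and 87.6/87.8% at s = −0.5. A further run put the loss from swapping at 0.6 to 0.8 points over slopes 0 to −0.5. With both covariates, the change from the planned model was −0.2 to +2.5 points, never a loss beyond Monte Carlo error.

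**Type I error.** With no true difference, rejection was 4.4% to 5.9% with tCFS and 4.5% to 5.9% with Dryness (Monte Carlo standard error √(0.05 × 0.95/3,000) = 0.4 points).

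**The case against.** The strongest reply is that this is preference. The three statements of the rule agree with one another, and no principle obliges an odds ratio and a mean difference to share a covariate. The test is valid, the endpoint is an other pre-specified one, and the planned Pearson chi-squared analysis gives a Dryness responder result that uses no baseline at all. A reason for tCFS may also exist where we cannot see it: Protocol 10.4.8 and 10.4.9 and SAP 6.5.7.5 appear in the contents lists but not in the text, and Protocol 4.5 is largely redacted. All of this stands, and it is why the point is minor.

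It also stands that a straight swap is not sure to help. If tCFS predicts Dryness change, the swap can lose up to about 1 point. That is a reason to allow both covariates. It does not favour leaving out baseline Dryness.

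A reader might infer three stronger things, and the documents support none of them:

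- **That the protocol and SAP contradict themselves, or that the result is biased.** They do not, and randomisation protects the test whichever baseline is used.
- **That the omitted stratification factors are at issue.** SAP 6.5.8.5 leaves them out openly; this point does not reopen that.
- **That the gain is large.** This needs a strong correlation between change and baseline, such as −0.6, which the documents do not give. The Protocol synopsis takes its NVU-002 estimates from an "ANCOVA analysis with CFB to Day 57 as the response, baseline as a covariate and treatment as the fixed effect from NVU-002", so SD 28 may be a residual SD. The marginal SD would then be 28/√(1 − 0.36) = 35, and the slope of change −0.6 × 35/20 = −1.05. The Day 57 score would have slope 1 − 1.05 = −0.05, so subjects drier at baseline would end slightly less dry. That is implausible, and no gain should be quoted from it.

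**Conclusion.** The point holds as an optional improvement. Dryness Score responders are adjusted for baseline tCFS alone, with no reason in the visible text, while the continuous Dryness endpoint is adjusted for its own baseline. The expected benefit of using baseline Dryness Score is about 0 to 2 percentage points of power, and essentially none if percentage change hardly depends on baseline. These figures rest on the assumed baseline distribution, saline change and slope. The direction of a straight swap also depends on how prognostic tCFS is, which the documents do not say; including both covariates removes that uncertainty. Sample size, alpha and the primary and secondary tests are untouched.

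**What to change.** In the Protocol synopsis, Protocol 10.4.7 and SAP 6.5.7.4.2, state that tCFS responders are adjusted for baseline tCFS and Dryness Score responders for continuous baseline Dryness Score, with baseline tCFS kept as a second covariate if the sponsor expects it to be prognostic. Define `<BASELINE>` under the PROC LOGISTIC code in the same terms, adding a second term if both are used. If tCFS alone is intended for Dryness responders, say why and still define the placeholder.

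Limit the change to these two endpoints. Protocol 10.4.7 goes on: "Exploratory and other endpoints will be summarized and analyzed similarly to the other pre-specified endpoints". Some of those may have no baseline; the eyedrop acceptability questionnaire, for example, is collected only at Visit 4. Leave the present wording for any other proportion.

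The cost is one sentence in three places and one defining line, made as a documented amendment before database lock and unmasking. No new data, subjects or alpha are needed. One side effect should be stated: the Dryness odds ratio becomes conditional on baseline Dryness Score and may lie slightly further from 1. In the tabulated simulation the log odds ratio ranged from 0.546 to 0.576 with tCFS and from 0.574 to 0.586 with Dryness.
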